8.5 Pharmacodynamics

Pharmacodynamic parameters are not evaluated in this study.

8.6 Genetics

Genetics are not evaluated in this study.

8.7 Biomarkers

Biomarkers are not evaluated in this study.

8.8 Immunogenicity Assessments

Not applicable

8.9 Health Economics

Health economics parameters are not evaluated in this study.

9.0 STATISTICAL CONSIDERATIONS

9.1 Statistical Hypotheses

No formal statistical hypotheses are to be tested.

9.2 Analysis Sets

For the purposes of analysis, the following analysis sets are defined:

- Safety Analysis Set: All participants who have received one dose of study treatment (CS-1103 or placebo)
- Pharmacokinetic Analysis Set: All participants who have received one dose of CS-1103 and have at least 1 quantifiable plasma or urine postdose concentration, without protocol deviations or events expected to affect PK results

9.3 Statistical Analyses

9.3.1 General Considerations

The SAP will be developed and will describe the participant analysis sets to be included in the analyses, and procedures for accounting for missing, unused, and spurious data. This section focuses on the summary of the planned statistical analyses of the primary and secondary endpoints.

All analyses, summaries, and listings will be performed using SAS® software (Version 9.4 or higher). Results will be summarized by treatment and overall, where appropriate.

The following descriptive statistics will be used as applicable to summarize the study data unless otherwise specified:

- Continuous variables: Sample size (n), mean, standard deviation (SD), median, minimum (min), and maximum (max)
- Summaries for plasma CS-1103 concentrations will include the coefficient of variation and PK parameter summaries will also include the geometric mean (except for t_{max} , which will only be presented as min, median, max)
- Categorical variables: Frequencies and percentages

Individual participant data will be presented in listings.

All missing or incomplete safety and PK data, including dates and times, are treated as such. Missing test results or assessments will not be imputed. The handling of any missing, unused, and spurious data will be documented in the Clinical Study Report.

9.3.2 Pharmacokinetic Analyses

9.3.2.1 *PK Analysis*

The PK analysis will be performed on the PK Population. CS-1103 plasma concentrations and calculated plasma and urine PK parameters will be listed and descriptively summarized by treatment and scheduled time point, as applicable. Arithmetic mean (\pm SD) and individual CS-1103 plasma concentration versus time curves will be plotted on linear and semilogarithmic scale, and percent of dose recovered in urine over time will be presented graphically, as appropriate. Dose proportionality of PK parameters will be explored graphically and by using a power model, as appropriate.

Scatter plots of individual values and geometric means of PK parameters, $AUC_{(0-\text{inf})}$ (or $AUC_{(0-\text{last})}$, if $AUC_{(0-\text{inf})}$ is not calculable in most participant), C_{max} (and C_{EOI} , if appropriate) as well as dose-normalized exposure parameters versus dose will be presented (PK parameter definitions provided in [Table 4](#)). Geometric mean and individual cumulative percent CS-1103 excreted in urine versus time curves will also be presented on linear scale.

Further details with respect to the PK analysis will be provided in the SAP.

9.3.2.2 *PK-PD Analysis*

As an exploratory analysis, concentration-QT relationship will be assessed using linear mixed effects modeling. The details of the model will be provided in the SAP.

9.3.3 Safety Analyses

All safety analyses will be performed on the Safety Analysis Population. Adverse events will be coded using the latest version of the Medical Dictionary for Regulatory Activities (MedDRA). The overall number and percentage of participants with at least one AE (and SAE) will be tabulated. Placebo participants will be combined into 1 treatment cohort. Overall, AE data will be summarized by treatment received. The frequency of all treatment emergent AEs (TEAEs), TEAEs by severity as detailed in [Section 10.3](#). All TEAEs by relationship to study treatment, SAEs, TEAEs leading to death, and TEAEs leading to discontinuation of the study will be tabulated by Preferred Term (PT) and System Organ Class (SOC) for each treatment cohort. Summary statistics, including change from baseline, for vital signs, laboratory parameters, and ECG intervals will be provided by treatment, visit, and time point, as appropriate. Shift tables for laboratory parameters at each postbaseline visit will be tabulated against baseline results showing frequency of laboratory parameter observed normal range indicator (Low, Normal, High). For ECG results, appropriate outlier tabulations for QT and QTcF will also be presented by treatment. Outliers for QT and QTcF defined under outcome measures will be summarized using counts and percentages by treatment and sampling time, if appropriate and using participant-level maximum over time by treatment. The following categories will be presented by treatment and overall for CS-1103:

- Outlier QT and QTcF intervals (450-480 ms, 480-500 ms and >500 ms)
- Change from baseline in QT and QTcF intervals (30-60 ms and >60 ms)

Results of the physical examinations (including injection site assessment) and the AQS will be listed and if appropriate, summarized by treatment.

9.4 Interim Analysis

No formal interim analysis is planned. Preliminary PK parameters will be calculated using available quality-controlled CS-1103 concentrations and scheduled sampling times to support dose escalation decisions, as applicable.

9.5 Sample Size Determination

The sample size for this study is based upon precedent set by other Phase 1 studies to gain preliminary measure of safety and CS-1103 PK characteristics in a healthy participant population and not on statistical considerations of power while exposing as few participants as possible to the study treatment and procedures.

A sample size of 8 participants per dose level (6 active: 2 placebo) in this study design is expected to be sufficient to meet the objectives of this study.

10.0 SUPPORTING DOCUMENTATION AND OPERATIONAL CONSIDERATIONS

10.1 Appendix 1: Regulatory, Ethical, and Study Oversight Considerations

10.1.1 Regulatory and Ethical Considerations

This study will be conducted in accordance with the protocol and with the following:

- Consensus ethical principles derived from international guidelines including the Declaration of Helsinki and Council for International Organizations of Medical Sciences international ethical guidelines
- Applicable ICH GCP guidelines
- Applicable laws and regulations.

The protocol, protocol amendments, ICF, IB, and other relevant documents (e.g., advertisements) must be submitted to an IRB by the Investigator and reviewed and approved by the IRB before the study is initiated.

Any amendments to the protocol will require IRB approval before implementation of changes made to the study design, except for changes necessary to eliminate an immediate hazard to study participants.

Protocols and any substantial amendments to the protocol will require health authority approval prior to initiation except for changes necessary to eliminate an immediate hazard to study participants.

The Investigator will be responsible for the following:

- Providing written summaries of the status of the study to the IRB annually or more frequently in accordance with the requirements, policies, and procedures established by the IRB
- Notifying the IRB of SAEs, or other significant safety findings as required by IRB procedures
- Providing oversight of the conduct of the study at the study site and adherence to requirements of 21 Code of Federal Regulations (CFR), ICH guidelines, the IRB, and all other applicable local regulations

After reading the protocol, each Investigator will sign the protocol signature page and send a copy of the signed page to the Sponsor or representative. The study will not start at any study site at which the Investigator has not signed the protocol.

10.1.2 Adequate Resources

The Investigator is responsible for supervising any individual or party to whom the Investigator delegates study-related duties and functions conducted at the study site.

If the Investigator/institution retains the services of any individual or party to perform study-related duties and functions, the Investigator/institution should ensure this individual or party is qualified to perform those study-related duties and functions and should implement procedures to ensure the integrity of the study-related duties and functions performed and any data generated.

10.1.3 Financial Disclosure

Investigators and sub-Investigators will provide the Sponsor with sufficient, accurate financial information as requested to allow the Sponsor to submit complete and accurate financial certification or disclosure statements to the appropriate regulatory authorities. Investigators are responsible for providing information on financial interests during the course of the study and for 1 year after completion of the study.

10.1.4 Insurance

The Sponsor has obtained liability insurance, which covers this study as required by local law and/or national regulations and/or ICH guidelines, whichever is applicable. The terms of the insurance will be kept in the study files.

10.1.5 Informed Consent Process

Participants must be informed that their participation is voluntary. Participants will be required to sign a statement of informed consent that meets the requirements of 21 CFR 50, local regulations, ICH guidelines, privacy, and data protection requirements, where applicable, and the IRB or study site.

The medical record must include a statement that written informed consent was obtained before the participant was enrolled in the study and the date the written consent was obtained. The authorized person obtaining the informed consent must also sign the ICF.

Participants must be reconsented to the most current version of the ICF(s) during their participation in the study.

A copy of the ICF(s) must be provided to the participant.

A participant who is rescreened will sign another ICF and receive a new screening number.

10.1.6 Data Protection

- Participants will be assigned a unique identifier by the Sponsor. Any participant records or datasets that are transferred to the Sponsor will contain the identifier only; participant

names or any information which would make the participant identifiable will not be transferred.

- The participant must be informed that his/her personal study-related data will be used by the Sponsor in accordance with local data protection law. The level of disclosure must also be explained to the participant who will be required to give consent for their data to be used as described in the informed consent.
- The participant must be informed that his/her medical records may be examined by Clinical Quality Assurance auditors or other authorized personnel appointed by the Sponsor, by appropriate IRB members, and by inspectors from regulatory authorities.

10.1.7 Committees Structure

10.1.7.1 Safety Review Committee

A SRC has been appointed for this study. The SRC is a group of clinicians and/or scientists who are appointed to monitor the safety and scientific integrity of a human research intervention, and to make recommendations regarding for escalation to the next planned dose level, escalation to an intermediate dose (a dose lower than the next planned dose), repeating a dose level, suspension of the dose escalation until further review of study data can be made, as to whether the stopping rules have been met, or stop dose escalation and termination of the study, etc. The composition of the committee is dependent upon the scientific skills and knowledge required for monitoring the particular study.

The SRC will consist, at a minimum, of the Principal or Sub-Investigator, Medical Monitor, and Sponsor's qualified designee. The SRC is responsible for reviewing and evaluating blinded safety and PK data for the most recently dosed cohort, cumulatively obtained data, and subsequently at regularly scheduled meetings and for the dose selection during dose escalation. The committee may also meet in ad hoc meetings at its discretion as needed in response to events occurring in the study.

Participant safety will be continuously monitored by the SRC, which includes safety signal detection at any time during the study.

In addition, an early aggregated safety data review will be performed, the goal of which is to allow for a cautious, stepwise approach to study treatment administration/dose escalation. An initial sentinel safety review by an Investigator for this study is planned for the first 2 participants who are dosed in each of the 5 cohorts and have provided safety and tolerability data for 24 hours after administration of a single dose prior to dosing the remaining participants within each cohort (see [Section 4.1](#)).

All safety results for at least 48 hours and preliminary PK data through at least Day 2 (24 hours postdose) for at least 6 out of the 8 participants within a cohort will be summarized

and reviewed by the SRC for agreement of next steps in dose escalation, due to the short half-life of the compound.

In particular, data will be reviewed by the Sponsor for identification of events that would potentially contribute to a requirement to pause/stop dose escalation or the study. See [Section 4.6](#) for stopping criteria details.

Enrollment will be paused during the review. If a stopping rule is met, a decision will be made, based on the review, as to whether enrollment in the study will be allowed to resume.

Case unblinding may be performed for above reviews if necessary.

The details regarding SRC meeting frequency, data to be reviewed, the data review process, and information dissemination to clinical sites, are included in the SRC charter.

10.1.8 Dissemination of Clinical Study Data

The results of the study should be reported within 1 year from the end of the clinical study. Irrespective of the outcome, the Sponsor will submit to any relevant database a summary of the results of the clinical study within 1 year from the end of the global clinical study. It shall be accompanied by a summary written in a manner that is understandable to laypersons.

10.1.9 Data Quality Assurance

- All participant data relating to the study will be recorded on printed or eCRFs unless transmitted to the Sponsor or designee electronically (e.g., laboratory data). The Investigator is responsible for verifying that data entries are accurate and correct by physically or electronically signing the case report form (CRF).
- Guidance on completion of eCRFs will be provided in eCRF Completion Guidelines.
- The Investigator must permit study-related monitoring, audits, IRB review, and regulatory agency inspections and provide direct access to source data documents.
- Quality tolerance limits will be predefined in the Integrated Project Management Plan to identify systematic issues that can impact participant safety and/or reliability of study results. These predefined parameters will be monitored during the study, and important deviations from the quality tolerance limits and remedial actions taken will be summarized in the clinical study report.
- Monitoring details describing strategy, including definition of study critical data items and processes (e.g., risk-based initiatives in operations and quality such as risk management and mitigation strategies and analytical risk-based monitoring), methods, responsibilities, and requirements, including handling of noncompliance issues and monitoring techniques (central, remote, or on-site monitoring) are provided in the Study Monitoring Plan.
- Details of study monitoring, including action required due to SARS-CoV-2/COVID-19, will be included in a separate Study Monitoring Plan.

- The Sponsor or designee is responsible for the data management of this study, including quality checking of the data.
- The Sponsor assumes accountability for actions delegated to other individuals (e.g., contract research organizations).
- Records and documents, including signed ICFs, pertaining to the conduct of this study must be retained by the Investigator for 15 years after study completion unless local regulations or institutional policies require a longer retention period. No records may be destroyed during the retention period without the written approval of the Sponsor. No records may be transferred to another location or party without written notification to the Sponsor.

10.1.10 Source Documents

The Investigator/institution should maintain adequate and accurate source documents and study records that include all pertinent observations on each of the study site's participants. Source data should be attributable, legible, contemporaneous, original, accurate, and complete. Changes to source data should be traceable, should not obscure the original entry, and should be explained if necessary (e.g., via an audit trail).

Source documents provide evidence for the existence of the participant and substantiate the integrity of the data collected. Source documents are filed at the Investigator's site.

Data reported on the CRF or entered in the eCRF that are transcribed from source documents must be consistent with the source documents or the discrepancies must be explained. The Investigator may need to request previous medical records or transfer records, depending on the study. Also, current medical records must be available.

Definition of what constitutes source data and its origin can be found in the monitoring guidelines and eCRF completion guidelines.

The Investigator must maintain accurate documentation (source data) that supports the information entered in the CRF.

Study monitors will perform ongoing source data verification to confirm that data entered into the CRF by authorized study site personnel are accurate, complete, and verifiable from source documents; that the safety and rights of participants are being protected; and that the study is being conducted in accordance with the currently approved protocol and any other study agreements, ICH GCP, and all applicable regulatory requirements.

10.1.11 Study and Site Start and Closure

First Act of Recruitment

The study start date and first act of recruitment is the date on which the clinical study will be open for recruitment of participants.

Study/Site Termination

The Sponsor or designee reserves the right to close the study site or terminate the study at any time for any reason at the sole discretion of the Sponsor. Study sites will be closed upon study completion. A study site is considered closed when all required documents and study supplies have been collected and a study site closure visit has been performed.

The Investigator may initiate study site closure at any time, provided there is reasonable cause and sufficient notice is given in advance of the intended termination.

Reasons for the early closure of a study site by the Sponsor or Investigator may include but are not limited to:

For study termination:

- Discontinuation of further study treatment development

For study site termination:

- Failure of the Investigator to comply with the protocol, the requirements of the IRB or local health authorities, the Sponsor's procedures, or GCP guidelines
- Inadequate or no recruitment (evaluated after a reasonable amount of time) of participants by the Investigator
- Total number of participants included earlier than expected

If the study is prematurely terminated or suspended, the Sponsor shall promptly inform the Investigators, the IRBs, the regulatory authorities, and any contract research organization(s) used in the study of the reason for termination or suspension, as specified by the applicable regulatory requirements. The Investigator shall promptly inform the participant and should assure appropriate participant therapy and/or follow-up.

10.1.12 Publication Policy

The data generated by this study are confidential information of the Sponsor. The Sponsor will make the results of the study publicly available. The publication policy with respect to the Investigator and study site will be set forth in the Clinical Trial Agreement.

The results of this study may be published or presented at scientific meetings. If this is foreseen, the Investigator agrees to submit all manuscripts or abstracts to the Sponsor before submission. This allows the Sponsor to protect proprietary information and to provide comments.

The Sponsor will comply with the requirements for publication of study results. In accordance with standard editorial and ethical practice, the Sponsor will generally support publication of

multicenter studies only in their entirety and not as individual study site data. In this case, a coordinating Investigator will be designated by mutual agreement.

Authorship will be determined by mutual agreement and in line with International Committee of Medical Journal Editors authorship requirements.

10.2 Appendix 2: Clinical Laboratory Tests

The tests detailed in Table 6 will be performed by the CRU local laboratory.

Protocol-specific requirements for inclusion or exclusion of participants are detailed in [Section 5.0](#) of the protocol.

Additional tests may be performed at any time during the study as determined necessary by the Investigator or required by local regulations.

Table 8 Protocol-required Laboratory Tests

Laboratory Assessments	Parameters	
Hematology	Platelet count	White blood cell count with differential (absolute and percent):
	Red blood cell count	Neutrophils
	Hemoglobin	Lymphocytes
	Hematocrit	Monocytes
	Red blood cell indices:	Eosinophils
	Mean corpuscular volume (MCV)	Basophils
	Mean corpuscular hemoglobin (MCH)	
	Mean cell hemoglobin concentration (MCHC)	Red cell distribution width (RDW)
	%Reticulocytes	Mean Platelet Volume (MPV)
Clinical Chemistry ^a	Blood urea nitrogen (BUN)	Triglycerides
	Creatinine	Aspartate aminotransferase (AST)
	Glucose	Alanine aminotransferase (ALT)
	Gamma glutamyl transferase (GGT)	Alkaline phosphatase (ALP)
		Creatine kinase
	Magnesium	Creatine kinase MB fraction will be performed if clinically indicated
	Cholesterol	Chloride
	Potassium	Globulin
	Sodium	Amylase
	Calcium	Total, direct, and indirect bilirubin
	Lactate dehydrogenase	Total protein
	Albumin	Phosphate
	Uric acid	Carbon dioxide (bicarbonate)
	Estimated glomerular filtration rate (eGFR) Modification of Diet and Renal Disease (MDRD): (eGFR = $175 \times [\text{Serum Creatinine}]^{-1.154} \times [\text{Age}]^{0.203} \times [0.742 \text{ only if female}] \times [1.212 \text{ only if black}]$)	
Coagulation	International normalized ratio (INR)	Activated partial thromboplastin time (APTT)
	Prothrombin time (PT)	Thrombin time

Laboratory Assessments	Parameters			
		Fibrinogen		
Urinalysis, Complete	Color	Ketones		
	Appearance	Occult Blood		
	Specific Gravity	Protein		
	pH	Nitrite		
	Glucose	Leukocyte esterase		
	Microscopy (if clinically indicated) ^b			
Viral serology ^c	Human immunodeficiency virus (HIV) I and II Ag/Ab			
	Hepatitis B surface antigen (HBsAg)			
	Hepatitis C virus (HCV)			
Drugs of abuse and alcohol	Amphetamine/Methamphetamine	Opiates (morphine, codeine, heroin)		
	Ethanol	Benzodiazepines		
	Cannabinoids	Methadone metabolites		
	Cocaine metabolites	Barbiturates		
		Ecstasy (3,4-methylenedioxymethamphetamine)		
	Cotinine (urine)	Phencyclidine		
Other Tests	
 COVID-19 Test Follicle stimulating hormone (FSH) (as needed in women of nonchildbearing potential only)^c Highly sensitive serum human chorionic gonadotropin (hCG) pregnancy test^c Highly sensitive urine hCG pregnancy test^d 
The results of each test must be entered into the (e)CRF.
			
NOTES:				
^a Details of liver chemistry stopping criteria and required actions and follow-up assessments after liver stopping or monitoring event are given in Section 4.6 .				
^b If protein, blood, nitrites, or leukocyte esterase is abnormal it will reflex to microscopic testing.				
^c Screening only.				
^d Admission/Day -1, Follow-up/EOS Visit, and if pregnancy is suspected after dosing.				

Investigators must document their review of each laboratory safety report.

10.3 Appendix 3: AEs and SAEs: Definitions and Procedures for Recording, Evaluating, Follow-up, and Reporting for Study Treatment

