5.1 Inclusion Criteria

Participants are eligible to be included in the study only if all of the following criteria apply:

1. Provision of signed and dated, written informed consent prior to any study specific procedures.
2. Healthy male and/or female participants aged 18 to 55 years, inclusive.
3. A body mass index between 18.0 to 30.0 kg/m², inclusive, and a minimum body weight of 50 kg.
4. Females must be of nonchildbearing potential, must not be lactating, must have a negative serum pregnancy test at the Screening Visit, and must have a negative urine pregnancy test on admission to the study site CRU. The nonchildbearing potential of the female participant will be confirmed at the Screening Visit by fulfilling 1 of the following criteria (see [Section 10.4.1](#) for additional information):
 - Postmenopausal defined as amenorrhea for at least 12 months following cessation of all exogenous hormonal treatments and with follicle stimulating hormone (FSH) levels in the laboratory defined postmenopausal range.
 - Documentation of irreversible surgical sterilization by hysterectomy, bilateral oophorectomy or bilateral salpingectomy but not tubal ligation.
5. Male participants should be willing to use double barrier contraception, i.e., condoms and spermicide, from the day of dosing until at least 90 days after dosing with the study treatment (see [Section 10.4.2](#) for additional information).
6. Male participants must agree not to donate sperm from the day of dosing until at least 90 days after dosing with the study treatment.
7. Considered generally healthy upon completion of medical history, physical examination, vital sign measurements, ECG, and clinical laboratory test results in the opinion of an Investigator at Screening and Admission/Day -1.
8. Must agree to abstain from alcohol intake 48 hours before administration of the study treatment, during the confinement period of the study until after the final Follow-up/EOS Visit.
9. Able to comply with the protocol and attend all scheduled visits.

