5.2 Exclusion Criteria

Participants are excluded from the study if any of the following criteria apply:

1. History of any clinically important disease or disorder which, in the opinion of an Investigator, may either put the participant at risk because of participation in the study, or influence the results or the participant's ability to participate in the study.
2. History or presence of gastrointestinal, hepatic or renal disease or any other condition known to interfere with absorption, distribution, metabolism or excretion of drugs.
3. Estimated glomerular filtration rate $<90 \text{ mL/min/1.73 m}^2$ based on Modification of Diet and Renal Disease formula during Screening and on Admission/Day -1 ([Table 6](#)).
4. Any current active infections, including localized infections, or any recent history (within 1 week prior to study treatment administration) of active infections (including severe acute respiratory syndrome coronavirus 2 [SARS-CoV-2]), cough or fever, or a history of recurrent or chronic infections.
5. Administration of any vaccine (live and inactivated [e.g., inactivated influenza vaccines or SARS-CoV-2 vaccines]) are not allowed within 2 weeks of dosing and while on study is prohibited.
6. Any clinically significant illness, medical/surgical procedure or trauma within 4 weeks of the first administration of study treatment or planned surgical procedure during the study period.
7. Blood donation/blood loss greater than 500 mL during the 56 days prior to screening.
8. Any positive result at the Screening Visit for serum hepatitis B surface antigen (HBsAg), hepatitis C virus (HCV) antibody, and human immunodeficiency virus (HIV).
9. Abnormal vital signs, after at least 5 minutes remaining in the supine position at the Screening Visit and on Admission/Day -1, defined as any of the following:
 - Systolic blood pressure $>145 \text{ mmHg}$
 - Diastolic blood pressure $>95 \text{ mmHg}$
 - Heart rate <45 or $>100 \text{ bpm}$
10. Any clinically significant abnormalities in rhythm, conduction or morphology of the resting ECG, and any clinically important abnormalities in the 12-lead ECG as considered by the Investigator that may interfere with the interpretation of QTc interval changes.
11. Prolonged Fridericia QTcF $>450 \text{ msec}$ in males or $>470 \text{ msec}$ in females or shortened QTcF $<340 \text{ msec}$ or family history of long QT syndrome at the Screening Visit and on Admission/Day -1

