8.2.5 Clinical Safety Laboratory Tests

See [Table 6](#) in [Section 10.2](#) for the list of clinical laboratory tests to be performed and the SoA ([Section 1.3](#)) for the timing and frequency.

Local laboratories will be utilized to process and provide results for clinical laboratory tests allowing for immediate participant medical management. The Investigator must review the laboratory report, document this review, and record any clinically significant changes occurring during the study as an AE. All AEs require appropriate follow-up as described in Section 8.3). The laboratory reports must be filed with the source documents.

All laboratory tests with values considered abnormal and clinically significant from the time of study treatment administration to the end of the study should be repeated up to or until the values return to normal or baseline, or are no longer considered clinically significant by the Investigator or medical monitor. If clinically significant values do not return to normal/baseline within a period of time judged reasonable by the Investigator, the etiology should be identified, and the Sponsor notified.

All protocol-required laboratory tests, as defined in [Table 6 \(Section 10.2\)](#), must be conducted in accordance with the Laboratory Manual and the SoA ([Section 1.3](#)).

If laboratory values from non-protocol-specified laboratory tests performed at the institution's local laboratory require a change in participant management or are considered clinically significant by the Investigator (e.g., SAE or AE or dose modification), then the results must be recorded.

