16.4.1. Clinically Noteworthy ECG Criteria

Clinically noteworthy quantitative ECG measurements will be identified in accordance with the following criteria:

- Absolute values for QTcF will be classified as:
 - 450 msec and <=480 msec
 - > 480 msec and <=500 msec
 - > 500 msec
- Change from Baseline for QTcF will be classified as:
 - Increase from baseline >30 msec and <=60 msec
 - Increase from baseline >60 msec

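### The protocol's only eGFR formula is printed with a positive age exponent and no creatinine unit, so as printed it cannot support the exclusion cut-off of 90 (minor; check against the source page)

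*Protocol*

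**What the plan says.** Protocol Section 5.2, exclusion 3, sets the limit at eGFR below 90 mL/min/1.73 m², "based on Modification of Diet and Renal Disease formula during Screening and on Admission/Day -1", and refers to the table of protocol-required laboratory tests.

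That table is in Section 10.2 (Appendix 2). Its clinical chemistry block gives eGFR as 175 times creatinine and age terms, with a factor of 0.742 for women and 1.212 for Black participants. The creatinine and age terms are printed as "Serum Creatinine}]^{-1.154} \times [\text{Age}]^{0.203". The creatinine exponent carries a minus sign and the age exponent does not. No unit for creatinine is given.

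Neither document prints the formula again, corrects the sign or gives the unit. SAP Section 16.3 takes laboratory units from the local laboratory.

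On who produces the value, Protocol Section 8.2.5 says "Local laboratories will be utilized to process and provide results for clinical laboratory tests", and Section 10.2 says the listed tests "will be performed by the CRU local laboratory".

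**The concern.** An eligibility criterion should be reproducible from the text it cites. Here the cited formula makes estimated kidney function increase with age at the same creatinine, and its output does not fall on a scale where 90 can divide people.

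Exclusion 3 is the only numeric renal threshold for entry to a first-in-human study, and Section 5.0 allows no waivers of enrolment criteria. Urinary excretion and renal clearance of CS-1103 are secondary endpoints, so renal function at entry matters to the population being described. Anyone who programmed or hand-calculated the printed expression would reach wrong eligibility decisions. Their direction would depend on the unit used.

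**Working it through.** **Inputs from the documents.** Constant 175, creatinine exponent −1.154, age exponent +0.203, factors 0.742 (female) and 1.212 (Black): Protocol Section 10.2. Cut-off 90: Section 5.2, exclusion 3. Ages 18 to 55: Section 5.1. The documents give no worked eGFR value, so there is no stated figure to reproduce.

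**Assumptions, not in the documents.** Creatinine of 0.6 to 1.5 mg/dL (also 2.0), or 53 to 133 µmol/L. The reversed age sign is used for comparison only.

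**Formula.** eGFR = 175 × Cr^(−1.154) × Age^(s × 0.203) × sex factor × race factor, with s = +1 as printed and s = −1 for comparison.

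**Step 1: age effect, free of units.** As printed, (55/18)^0.203 = 1.2545, a rise of 25% from age 18 to 55. With the sign reversed, (55/18)^(−0.203) = 0.7971, a fall of 20%. The printed value exceeds the reversed one by Age^0.406, which is 3.2-fold at 18 and 5.1-fold at 55.

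**Step 2: range of results over ages 18 to 55 and all four sex and race groups.**

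| Creatinine (assumed) | As printed | Age sign reversed |
|---|---|---|
| 0.6 to 1.5 mg/dL | 146 to 863 | 36 to 213 |
| 2.0 mg/dL | 105 to 215 | 26 to 53 |
| 53 to 133 µmol/L | 0.8 to 4.9 | 0.2 to 1.2 |

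The lowest printed result at 1.5 mg/dL is a non-Black woman aged 18: 175 × 1.5^(−1.154) × 18^0.203 × 0.742 = 175 × 0.6263 × 1.7981 × 0.742 = 146. The highest at 0.6 mg/dL is a Black man aged 55: 175 × 1.8031 × 2.2558 × 1.212 = 863.

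As printed, nobody in the mg/dL range falls below 90, even at 2.0 mg/dL. In µmol/L everybody does. The last row also shows that the unit matters whichever sign is right.

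**Step 3: creatinine at which eGFR equals 90.** Cr90 = (175 × Age^(s × 0.203) × factors / 90)^(1/1.154), read as mg/dL, at age 18 then age 55:

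| Group | As printed | Age sign reversed |
|---|---|---|
| Non-Black women | 2.28, 2.78 | 0.83, 0.68 |
| Black women | 2.70, 3.28 | 0.98, 0.80 |
| Non-Black men | 2.96, 3.60 | 1.07, 0.88 |
| Black men | 3.49, 4.25 | 1.26, 1.04 |

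As printed, the limit lies at 2.28 to 4.25, above the whole assumed mg/dL range. With the sign reversed it lies at 0.68 to 1.26, inside that range, so 90 separates people.

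**The case against.** **The fault may not be in the protocol.** It rests on one superscript minus in text read from a PDF, and that reading is visibly imperfect. Section 2.2 contains a meaningless table in place of a figure. Table captions do not match the list of tables. In SAP Section 16.4.1 the first QTcF class appears as "450 msec and <=480 msec", without the greater-than sign that the next two classes carry. This stands: a lost sign cannot be ruled out. Against it, the minus on −1.154 survived in the same expression, and the missing unit does not depend on the sign.

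**The correct sign is not in the documents.** Exclusion 3 names MDRD but prints no equation. This also stands. The reversed sign is a comparison, and the protocol's own age range and cut-off show the problem without it, given an assumed creatinine range in either unit.

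**The laboratory calculates eGFR.** Sections 8.2.5 and 10.2 place testing with the local laboratory, no section tells site or programming staff to compute eGFR, and the SAP derives none. Mistaken use would be conspicuous: at 1.0 mg/dL every participant would score 234 to 478. There are other safeguards too. "Investigators must document their review of each laboratory safety report" (Section 10.2); exclusion 2 covers "History or presence of gastrointestinal, hepatic or renal disease"; inclusion 7 requires that volunteers be "Considered generally healthy upon completion of medical history" and other examinations; and creatinine itself is reported. This largely stands and is why the point is minor. These safeguards are qualitative, however, and the documents do not say which equation the laboratory has programmed.

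**A stronger reading to avoid.** A reader might infer that exclusion 3 did not operate, that people with reduced renal function were enrolled, or that renal clearance results are compromised. The documents do not support this. Nothing shows that the printed expression was used, excluding nobody is only the mg/dL branch, and renal clearance is calculated from the amount excreted and AUC, not from eGFR.

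**Conclusion.** The point holds as a minor defect in the text. The formula to which exclusion 3 points, as it reads in the available text, has a positive age exponent and no creatinine unit, and it cannot separate people at 90 in either mg/dL or µmol/L. The 25% rise with age needs no assumption; the failure at 90 rests on the assumed creatinine ranges, but the margin is wide in both units.

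Two conditions limit it. The sign must be confirmed on the source page. Eligibility is touched only if the printed expression was actually used, which is unlikely. No endpoint, analysis or sample size depends on the formula.

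**What to change.** Check the sign of the age exponent in Section 10.2 against the source page and against the MDRD equation programmed by the local laboratory. If they differ, correct the printed formula. State the creatinine unit in either case. Re-check exclusion 3 only for participants whose eGFR came from the printed version. The cut-off of 90 is unchanged.

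The cost is one look at the source page, one query to the laboratory, one unit and at most one sign in the table. The design does not change, and if the laboratory reported its own MDRD value no eligibility decision changes.
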